1.4. Sample Size Determination

The study was powered to test the primary endpoint of the study.

The sample size was computed assuming a response rate of 30% at 48 weeks for Arm B (placebo + prednisone). A sample size of 186 randomized subjects provides at least 80% power to detect a 20% difference in the response rates at 48 weeks between the 2 treatment arms at an alpha level of 5% (2-sided).

No replacement of subjects was implemented.

The sample size and power calculations were produced using the software package, East (Cytel Software Corp, Cambridge, MA).

1.5. Planned Analyses

1.5.1. Interim Analysis

No interim efficacy analysis was performed by the sponsor. An interim futility analysis was performed by the DMC after the first 50 subjects were enrolled and their response at week 24 was established.

1.5.2. Primary Analysis

The primary analysis will be performed approximately one year after enrollment of the last subject.

1.5.3. Final Analysis

After the primary analysis the sponsor will continue to follow the subjects for an additional year to further quantify response for subjects on the study treatment and to assess OS. In addition, withdrawal of all systemic therapies for cGVHD (including ibrutinib/placebo) will be assessed.

The final analysis will be performed approximately two years after enrollment of the last subject.

1.6. Testing Procedure and Level of Significance in the primary analysis

To preserve the study wise type I error rate of 0.05, the primary and secondary endpoints will be tested based on a serial gatekeeping testing procedure at the two-sided significance level of 0.05 according to the hierarchical order specified below:

1. Response rate at 48 weeks
2. Time to withdrawal of all corticosteroids for treatment of cGVHD
3. Time to withdrawal of all ISTs, including corticosteroids for treatment of cGVHD (with the exception of ibrutinib/placebo)
4. Response rate at 24 weeks
5. Improvement in Lee cGVHD Symptom Scale at 2 consecutive visits
6. Proportion of subjects who achieve reduction of corticosteroids dose level to less than 0.15 mg/kg/d at 24 weeks sustained for at least 30 days

Since the number of deaths at the primary analysis is expected to be low, formal analysis for OS will be performed at the final analysis. However, summary of OS will be provided based on available data at the time of the primary analysis. Duration of response will be analyzed to support the response endpoints.

1.7. Blinding and Randomization Methods

1.7.1. Blinding Method

This is a double-blind study; the subjects, the investigators, and the Sponsor are blinded to the treatment assignment.

1.7.2. Randomization Method

Central randomization was implemented in this study. Subjects were randomized based on the following stratification factors:

- Age group (12 to <22 years old vs ≥ 22 years old)
- NIH Global Severity grade (moderate vs. severe)
- Ongoing use of systemic immunosuppressants that were initiated for either treatment of or prophylaxis for acute GVHD (yes vs. no)

Subjects were randomized in a 1:1 ratio to either Treatment Arm A or Treatment Arm B within each randomization stratum. This randomization scheme was implemented within the Interactive Web Response System (IWRS).

2. GENERAL ANALYSIS CONSIDERATION

2.1. Analysis Sets

2.1.1. Intent-to-Treat Population (ITT)

The intent-to-treat (ITT) population includes all randomized subjects. Subjects in the ITT population will be analyzed according to the treatment to which they were randomized. The ITT population will be the primary population for the analyses of efficacy endpoints (except for duration of response), all baseline characteristics, and patient reported outcome (PRO) endpoints.

2.1.2. Modified Intent-to-Treat Population (mITT)

The mITT population will include all ITT subjects who do not have evidence of progression of underlying malignancy at or before randomization. The mITT population will be used for sensitivity analyses of the primary efficacy endpoints.

2.1.3. Safety Population

Subjects in the ITT population who received at least one dose of either ibrutinib or placebo will be included in the safety population. Subjects in the safety population will be analyzed according to the actual treatment received and will be used to summarize the safety (including dosing) data.

2.1.4. Pediatric Population

The pediatric population includes the subset of the ITT population who were <18 years of age at the time of randomization. Summary or listing of the primary endpoint and selected secondary endpoints will be produced for the pediatric population as appropriate.

2.1.5. Definition of Subgroups

Subgroup analyses will be performed for the selected variables to assess the internal consistency of the treatment benefit and/or safety. The subgroup variables and the cutoff values are subject to change if warranted to better represent the data.

Table 1. Subgroup Definition

Subgroup	Definition of Subgroup	Analysis Type
Age	<65 years, ≥65 years	D, E, S
Sex	Male, Female	D, E, S
Race	White, Non-White	D, E, S
Geographic region	US, Non-US	D, E, S
NIH Global cGVHD Severity grade	Moderate, Severe	D, E, S
Ongoing use of systemic immunosuppressants at enrollment that were initiated for either treatment of or prophylaxis for GVHD	Yes, No	D, E, S
Hepatic impairment (Based on NCI ODWG liver function classification)	Yes, No	D, S
Renal impairment	Yes, No	D, S
analysis type D= demographic and baseline disease characteristics analysis type E= efficacy analysis type S= safety		

3. SUBJECT INFORMATION

Subject information will be summarized descriptively with no formal testing performed. Summaries will be presented by arm (ibrutinib+ prednisone vs placebo + prednisone).

3.1. Subject Disposition

Subject randomization will be summarized by region, country, site and by stratification factors. Subject disposition for each study treatment (for ibrutinib/placebo and for prednisone) and for study participation will be tabulated.

Time on study is defined in the same way as overall survival with reversed censoring, i.e., subjects who died will be censored at death date. The Kaplan-Meier methodology will be used to estimate the median time on study.

3.2. Demographics and Baseline Characteristics

Demographic information and baseline characteristics will be summarized using descriptive statistics for ITT population by treatment arm. Demographic information includes age, gender, race, ethnicity, and geographic region. Baseline disease characteristics include time from initial diagnosis of cGVHD, cGVHD staging (moderate, severe), acute GVHD history, ongoing use of immunosuppressants, donor HLA matching, Karnofsky performance score, organs involved, primary disease (i.e., the disease that was indication for the transplant) and time from transplant to cGVHD diagnosis.

3.3. Prior and Concomitant Medications

Medications will be coded to preferred term and Anatomical Therapeutic Chemical (ATC) class according to World Health Organization (WHO) Drug dictionary where applicable.

Prior medications are defined as medications that started prior to the first dose date of study drug (ibrutinib/placebo). Concomitant medications are defined as medications that were taken at any time on treatment (i.e. from the date of the first dose of study drug through the date of the last dose of study drug).

Concomitant medications will be summarized by therapeutic class and preferred term and by treatment arm for all subjects in the safety population. Each subject will be counted once for each preferred term, and each therapeutic class.

The following medications will be summarized separately for the safety population:

- Prior acute GVHD treatment
- Prior GVHD prophylactic treatment
- Concomitant medications
- The following concomitant medications of special interest will be summarized separately:
 - Systemic immunosuppressants other than prednisone
 - Cyp3A Inhibitors (moderate, strong)
 - Cyp3A Inducers
 - Anticoagulants and antiplatelets
- Subsequent systemic cGVHD treatment

3.4. Extent of Exposure to Study Treatment

Exposure to study treatment will be summarized for ibrutinib/placebo and for prednisone by treatment arm for the safety population.

Prednisone daily dosing will be summarized over time. Duration of prednisone treatment and total dose received will be summarized

The following parameters will be summarized for the study drug ibrutinib/placebo:

- Treatment duration
- Relative dose intensity
- Number (%) of subjects with dose reduced due to AE

4. EFFICACY

Analysis of efficacy endpoints will be conducted on the ITT population, unless otherwise specified. Table 2 summarizes the efficacy endpoints and analysis methods to be performed. For subgroup and exploratory analyses, the analyses will be performed where appropriate.

An unstratified analysis will be performed for the primary endpoint, because only 8 subjects aged 12 to <22 years were enrolled, which may result in half of the strata with only a few or possibly no subjects randomized to a particular treatment arm. In addition, errors in the assignment of stratification factors into the IWRS for both cGVHD severity and ongoing use of immunosuppressants occurred at the site level in the study.

Table 2. Efficacy Endpoints definition and Analyses

Endpoint	Definition	Analysis Method	Population
Primary Endpoint			
Response Rate at 48 Weeks	
Proportion of responders [complete response (CR) or partial response (PR)] as assessed by investigators at 48 weeks using the NIH Consensus Panel Chronic GVHD Activity Assessment.
 
A subject will NOT be considered as a responder at 48 weeks if he/she meets any of following criteria:
 
 Starts a second line systemic therapy for cGVHD at or prior to the response assessment at 48 weeks Has evidence of progression of the underlying malignancy that was the indication for transplant at or prior to response assessment at 48 weeks Subjects withdrawing from the study or from response assessment prior to 48 weeks. 	
Unstratified Chi-square test
 
Subgroups (from Table 1) Comparison of the treatment arms within each subgroup using p-values from unstratified Chi square test and graph of Odds Ratio (95% CI) for each subgroup.
	
ITT
 
For mITT and Pediatric population, summary or listing will be provided as appropriate

Secondary Endpoints			
Time to withdrawal of all corticosteroids for treatment of cGVHD	
Time from randomization until the date of complete withdrawal (to 0mg) of corticosteroids used to treat GVHD and sustained for 30 days. Subjects will be considered having a competing risk at the time of death, relapse of the underlying disease, progression of cGVHD, or start of subsequent cGVHD therapy. Subjects with no competing event will be censored at last available study visit.
	
The two Cumulative Incidence Functions (CIFs) of corticosteroid withdrawal will be compared using Gray's Chi square test.
 
Graphs of the CIFs and landmark estimates (95%) at 6 months and 12 months
	ITT

Endpoint	Definition	Analysis Method	Population
		obtained from the CIFs will be provided.	
Time to withdrawal of all ISTs, including corticosteroids for treatment of cGVHD (with the exception of ibrutinib/placebo)	Time from randomization until the date of complete withdrawal (to 0mg) of all corticosteroids used to treat GVHD AND discontinuation of all ISTs sustained for 30 days. Subjects will be considered having a competing risk at the time of death, relapse of the underlying disease, progressive disease (PD) of cGVHD, or start of subsequent cGVHD therapy. Subjects with no competing event will be censored at last available study visit	The two CIFs of withdrawal of all immunosuppressants will be compared using Gray's Chi square test. Graphs of the CIFs and landmark estimates (95%) at 6 months and 12 months obtained from the CIFs will be provided	ITT
Response rate at 24 weeks	
Proportion of responders [complete response (CR) or partial response (PR)] as assessed by investigators at 24 weeks using the NIH Consensus Panel Chronic GVHD Activity Assessment.
 
A subject will NOT be considered as a responder at 24 weeks if he/she meets any of following criteria:
 
 Starts a second line systemic therapy for cGVHD at or prior to the response assessment at 24 weeks Has evidence of progression of the underlying malignancy that was the indication for transplant at or prior to response assessment at 24 weeks 
Subjects withdrawing from the study or from response assessment prior to 24 weeks.
	Comparison of the proportions between the two arms will be performed using Chi-square test	ITT
Improvement in overall score on Lee cGVHD Symptom Scale	
Proportion of subjects who had Lee total score decreasing at least 7 points at 2 consecutive visits with no PD, relapse of underlying disease or start of subsequent cGVHD treatment.
 
Proportion of subjects who had Lee total score decreasing at least 7 points at any time during the study (not preceded by PD, relapse of underlying disease or start of subsequent cGVHD treatment)
	
Comparison of the proportions between the two arms will be performed using chi-square test.
 
Supportive: Summary of the proportions of subjects with at least 7 points improvement at any
	ITT

Endpoint	Definition	Analysis Method	Population
	Mean Lee scores overtime	time will be provided. Summary of mean Lee scores overtime and graphs by treatment arm will be provided	
Proportion of subjects who achieve reduction of corticosteroids dose level to less than 0.15 mg/kg/d at 24 weeks sustained for at least 30 days	Proportion of subjects with prednisone equivalent dose reduction to a level of less than 0.15 mg/kg/d for a duration of at least 30 days at 24 weeks Mean daily corticosteroid dosing overtime	Comparison of the proportions between the two arms will be performed using Chi-square test Supportive: Mean (95%CI) of daily corticosteroid dosing over time will be summarized and plotted by arm	ITT
Duration of response	The interval between the date of initial documentation of a response (PR or better), and the date of first documented evidence of progressive cGVHD, relapse of underlying disease, start of subsequent cGVHD treatment, or death for responders only.	DOR will be estimated by Kaplan-Meier methodology: median DOR and landmark estimates with 2-sided 95% CIs will be provided for each treatment arm. K-M plots will be provided	Responders include subjects with response at any time during study treatment
Overall Survival	Time from the date of randomization until the date of death due to any cause. All deaths observed at the time of the data extraction date will be considered as events. For subjects who were not known to have died at the time of the analysis, OS data will be censored at date last known alive.	Survival will be estimated by Kaplan-Meier methodology: median OS and landmark estimates with 2-sided 95% CIs will be provided for each treatment arm. Kaplan-Meier plots will be provided	ITT
Exploratory Endpoints			

Endpoint	Definition	Analysis Method	Population
Improvement in SF-36 patient reported outcome	SF-36 subscales over time for each treatment arm	Descriptive summary statistics mean and 95% CI for each timepoint	ITT
Improvement in Karnofsky performance scale score	Karnofsky scores over time for each treatment arm	Descriptive summary statistics mean and 95% CI for each timepoint	ITT

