### **9.2. Discontinuation from Ibrutinib/Placebo**

Ibrutinib/placebo will be discontinued in the event of any of the following events:

- Subject begins treatment with another systemic therapy (including ECP) for cGVHD
- cGVHD progression
- Progression or relapse of the malignancy that was the indication for transplantation or development of PTLD
- Unacceptable toxicity: an intercurrent illness or AE that prevents further ibrutinib/placebo administration despite dose adjustment
- Noncompliance with study medication
- Investigator's decision (such as chronic noncompliance, significant protocol deviation, or best interest of the subject)
- Withdrawal of consent for treatment by subject
- Unblinding at primary efficacy analysis
- Study termination by Sponsor
- Subject becomes pregnant
- Death

All subjects, regardless of reason for discontinuation of ibrutinib/placebo will undergo an End-of-Treatment visit and be followed as outlined under [Section 8.3](#).

The investigator should notify the Sponsor within 24 hours if a subject discontinues ibrutinib/placebo treatment due to cGVHD progression and should provide documentation of cGVHD progression for review by the Sponsor's medical monitor.

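### The subgroup analyses aim to show consistency of benefit, but the SAP compares arms only within each level and sets no date for fixing the subgroup definitions

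*SAP*

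**What the plan says.** SAP section 2.1.5 states the purpose: "Subgroup analyses will be performed for the selected variables to assess the internal consistency of the treatment benefit and/or safety". Its Table 1 marks six two-level factors for efficacy: age, sex, race, region, NIH severity and ongoing immunosuppressant use. The section then adds: "The subgroup variables and the cutoff values are subject to change if warranted to better represent the data".

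The method for the primary endpoint is in SAP Table 2 (section 4): "Comparison of the treatment arms within each subgroup using p-values from unstratified Chi square test and graph of Odds Ratio (95% CI". The SAP contains no interaction term, heterogeneity test or ratio of odds ratios, and protocol section 10 describes no efficacy subgroup analysis.

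On error control, SAP section 1.6 says "the primary and secondary endpoints will be tested based on a serial gatekeeping testing procedure at the two-sided significance level of 0.05"; subgroup p-values are not part of that procedure.

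On blinding, SAP section 1.7.1 says "This is a double-blind study; the subjects, the investigators, and the Sponsor are blinded to the treatment assignment". Protocol section 9.2 lists "Unblinding at primary efficacy analysis" among the reasons for stopping ibrutinib/placebo. SAP section 1.5.2 puts the primary analysis about one year after the last enrolment. For the final analysis, section 1.5.3 says: "The final analysis will be performed approximately two years after enrollment of the last subject".

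**The concern.** Consistency is a question about the difference in effect between levels. A p-value computed inside one level answers another question: whether that level alone has enough subjects, and enough luck, to reach significance. In a trial sized for about 80% power overall, neither level of a factor is well powered. A uniform benefit will therefore often be significant in one level and not in the other, and this can be read as benefit confined to one group.

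The odds-ratio plot is useful, but no overall reference line is specified and it stands beside the p-values. Readers will tend to compare each interval with 1, which leads to the same misreading.

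The second part is timing. Section 2.1.5 does not confine changes of variable or cutoff to the period before unblinding. Because the blind ends at the primary analysis and a final analysis follows about a year later, blinding alone sets no deadline. The SAP does not describe any search over cutoffs, and none is alleged here.

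**Working it through.** **Inputs.** Control response 30%, a 20-point difference (so 50% on ibrutinib), at least 80% power and N=186, with the comparison "between the 2 treatment arms at an alpha level of 5% (2-sided") (SAP 1.4); 193 subjects enrolled, 1:1 (SAP 1.1); six two-level efficacy factors (SAP Table 1). The documents give no level sizes, so splits from 50/50 to 10/90 are assumed.

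**The plan's own figure.** For n per arm, power = Φ{[0.20·√n − 1.96·√(2·0.4·0.6)] / √(0.5·0.5 + 0.3·0.7)} = Φ{[0.20·√n − 1.358] / 0.678}. With n=93: (1.929 − 1.358)/0.678 = 0.84, power 80.0%. The planned 186 reproduces. With 193 subjects (96.5 per arm) power is 81.5%.

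**Same effect in both levels, by formula (N=193).** With level powers a and b, the chance that exactly one level is significant is a(1−b) + b(1−a). At 50/50, n=48.25 per arm per level: (1.389 − 1.358)/0.678 = 0.046, power 52%, and 2·0.518·0.482 = 50%. At 20/80, powers are 24% and 72%, giving 0.240·0.278 + 0.722·0.760 = 62%.

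| Split | Power, smaller / larger level | Exactly one p<0.05 | Both p<0.05 |
|---|---|---|---|
| 50/50 | 52% / 52% | 50% | 27% |
| 30/70 | 34% / 66% | 55% | 22% |
| 20/80 | 24% / 72% | 62% | 17% |
| 10/90 | 14% / 77% | 70% | 11% |

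**By simulation** (100,000 trials per cell, 97 vs 96 subjects, random level membership, Pearson chi-square in each level), exactly one level is significant under a uniform effect in:

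| Ibrutinib rate (control 30%) | Range over splits 50/50 to 10/90 |
|---|---|
| 40% | 29–32% |
| 45% | 45–53% |
| 50% (design) | 50–69% |
| 55% | 42–75% |
| 60% | 25–72% |

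Reading each level's 95% CI against 1 gives nearly the same at the design effect: 50–72%. Deleting the p-values alone would therefore not cure the problem.

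**Does the pattern carry information?** Compare a uniform 30% vs 50% effect with an effect absent in one level (30% vs 30% there). The interaction test is a Wald test on the difference in log odds ratios, with 0.5 added to each cell.

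| Split | Split significance: uniform | Absent in one level | Interaction flagged: uniform | Absent in one level |
|---|---|---|---|---|
| 50/50 | 50% | 52% | 5% | 27% |
| 20/80 | 61% | 70% (smaller level), 27% (larger level) | 4% | 18% |
| 10/90 | 69% | – | 3% | 8–10% |

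At 50/50 the pattern barely separates the two truths. At 20/80 it becomes less frequent when the larger level has no benefit.

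**Six factors together** (20,000 trials, six independent factors, five assumed sets of level shares). Under a uniform effect at least one factor is split by p-value in 86–93% of trials at 30% vs 50%, and in 56–98% across the five effect sizes. At least one unadjusted interaction is flagged in 21–26%; for six independent tests, 1 − 0.95^6 = 26%. If level CIs are read against the overall odds ratio instead, they exclude it for 1–2% of factors (4–11% for any of six).

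**Precision of the ratio of odds ratios.** The variance of a level's log odds ratio is [1/0.3 + 1/0.7 + 2/0.5]/n = 8.76/n. At 50/50 the SE of the difference is √(2·8.76/48.25) = 0.603, so the CI runs a factor exp(1.96·0.603) = 3.3 each way. At 10/90 the SE is √(8.76/9.65 + 8.76/86.85) = 1.004, a factor of 7.2 (about 7.3 in simulation). The ratio needed for 80% interaction power is exp(2.80·0.603) = 5.4 at 50/50 and about 17 at 10/90.

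**The case against.** The strongest reply is that this is a presentation matter. No decision rule uses subgroup p-values, the analyses are exploratory in practice, and the planned plot shows both odds ratios with their CIs, so a reader can judge consistency by eye or derive the ratio. The interaction test is also weak here: 18–27% power at splits from 50/50 to 20/80 even when benefit is absent in one level, with a false flag somewhere among six factors in 21–26% of trials. Much of this stands. It limits the harm to interpretation and means the ratio of odds ratios must be presented as an imprecise estimate. It does not make within-level p-values answer the question the SAP sets.

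Two points narrow the argument. At a 50/50 split the discordance comes from chance and limited power, not from unequal level sizes. And the 50% against 52% comparison is not at a fixed overall effect, because removing the effect from half the subjects also halves the overall difference.

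The magnitudes rest on assumed splits and, in the main runs, equal control rates. With control rates of 20% and 40% in the two levels, the split pattern still occurs in half of trials or more under a uniform effect.

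On timing, Table 1 names every variable and cutoff, the sponsor is blinded until the primary analysis, and the SAP does not say that Week 48 subgroups will be repeated at the final analysis. This is the weaker half of the point. The change clause still carries no limit.

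**Conclusion.** The point holds. The planned subgroup method does not address the stated aim, and nothing else in the protocol or SAP supplies a between-level estimate. Under a uniform design effect a misleading split should be expected for any one factor in about half to two-thirds of trials, and for at least one of six factors in roughly nine trials in ten. These figures assume 193 subjects, 30% control response and level splits from 50/50 to 10/90; the any-of-six figure also assumes independent factors. The harm is minor to moderate and confined to interpretation. The missing freeze point for definitions is a smaller gap of wording. The change should be made, but the trial's primary conclusion does not depend on it.

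**What to change.** In SAP Table 2:

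- Delete the within-level p-values.
- Keep the odds-ratio plot and add the overall odds ratio as a reference line.
- For each factor, report the ratio of odds ratios with its 95% CI from a logistic model with a treatment-by-subgroup term. The interaction p-value may be shown beside it. Label both exploratory and unadjusted.
- Add a note that a level's CI crossing 1 does not show inconsistency, and that a non-significant interaction does not show consistency.

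In SAP section 2.1.5, fix the variables and cutoffs before unblinding for the primary analysis and label any later change post hoc.

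The cost is a few sentences and one model per factor on data already collected. The drawback is the imprecision shown above: wide intervals, low power, and an expected false flag among six unadjusted tests in about one trial in four or five.

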### 1.1.2. Current Treatment Options

Available therapy for cGVHD is primarily broad-spectrum immunosuppressants which increase the risk of infections and tumor relapse by inhibiting GVT immunity (Holler 2007). The initial and current standard of care treatment for cGVHD is corticosteroids. However, more than 50% of the patients eventually relapse or become refractory, requiring second-line treatment, for which there is no standard of care. Recently, ibrutinib received approval in the United States for the treatment of adult patients with cGVHD after failure of one or more lines of systemic therapy.

Treatment with immunosuppressants is typically needed for a median duration of 2 to 3 years, further contributing to morbidity (Syrjala 2012). During that time patients are likely to experience some or all of the side effects of corticosteroids which include more frequent infections, hypertension, hyperglycemia, decrease in bone density, avascular necrosis, adrenal insufficiency, cataracts and disturbed sleep patterns (Sullivan 1988, Rayos [Prednisone] USPI 2013). Because of the frequent morbidity associated with prolonged corticosteroid use, many other immunosuppressant agents have been investigated in cGVHD, both in the front line and second line setting. Several controlled, phase 3 studies where these agents have been added on to corticosteroid therapy were all unsuccessful in providing benefit despite showing efficacy in early phase studies (Gilman 2012, Martin 2009, Koc 2002, Arora 2001, Koc 2000, and Sullivan 1988). An analysis of clinical trial quality measures in 60 trials in cGVHD primarily conducted before the NIH standardized response criteria (Pavletic 2006) were developed,

revealed that poor study design (eg, lack of rigorous entry criteria, organ response criteria and overall response criteria) likely biased efficacy in the early phase trials (Martin 2011) thereby leading to later unsuccessful controlled studies with the same agents. Agents such as cyclosporine, tacrolimus, sirolimus, and/or mycophenolate mofetil are often added to corticosteroid therapy in both frontline and second line settings despite the lack of efficacy. There is a lack of standard of care and high unmet need for new therapeutic options to effectively suppress immune and fibrotic cascades while preserving GVT and immunity against infection.

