### **6.1.2. Systemic Immunosuppressant Therapy**

During the Screening period, the physician will have the discretion to start prednisone while eligibility for the study is being confirmed, however, the subject must be randomized within 7 days of initiating treatment with prednisone.

Addition of any other new systemic immunosuppressant therapy (including ECP) to treat cGVHD is prohibited during Screening and subsequent enrollment into the study. Addition of a new systemic immunosuppressant for cGVHD will be considered a treatment failure and ibrutinib/placebo will be discontinued.

At enrollment, subjects may be receiving other immunosuppressants for the prophylaxis or treatment of acute GVHD. Tapering of these other immunosuppressants upon start of ibrutinib/placebo or prednisone is permitted (see [Section 5.3.2.2.1](#)).

Use of immunosuppressants for reasons other than treatment for cGVHD should be discussed with the medical monitor.

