6. MODIFICATIONS OF ANALYSIS TO THE PROTOCOL

- New secondary endpoint added: “Time to withdrawal of all corticosteroids for treatment of cGVHD sustained for at least 30 days”. For all endpoints that involve corticosteroid or IST withdrawal, the period of withdrawal had to be sustained for 30 days.
- Karnofsky scores will be analyzed as an exploratory efficacy endpoint in this SAP rather than as a safety endpoint as stated in the study protocol.

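### The two withdrawal endpoints (gated tests 2 and 3) have no rule for a relapse, progression or new therapy inside the 30-day window, so read literally such subjects can count as successes

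*SAP*

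**What the plan says.** SAP Section 1.6 tests six endpoints in a fixed order at two-sided 0.05. Withdrawal of corticosteroids is second and withdrawal of all immunosuppressants (ISTs) is third.

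Table 2 in SAP Section 4 defines the second endpoint as "Time from randomization until the date of complete withdrawal (to 0mg) of corticosteroids used to treat GVHD and sustained for 30 days". The third uses the same steroid criterion "AND discontinuation of all ISTs sustained for 30 days". Both rows then say: "Subjects will be considered having a competing risk at the time of death, relapse of the underlying disease, progression of cGVHD". Each list ends with the start of subsequent cGVHD therapy. Otherwise, "Subjects with no competing event will be censored at last available study visit". The arms are compared on cumulative incidence functions (CIFs) with Gray's test, and landmark estimates are reported at 6 and 12 months.

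SAP Section 6 restates the condition for every endpoint involving steroid or IST withdrawal: "the period of withdrawal had to be sustained for 30 days". It does not mention event-free status.

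The Lee symptom-scale row of the same table, also confirmed over time, does have such a condition. Improvement must hold "at 2 consecutive visits with no PD, relapse of underlying disease or start of subsequent cGVHD treatment".

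Nothing elsewhere fills the gap. Protocol Section 10.4.2 lists IST withdrawal without defining the event, the steroid endpoint was added in the SAP, and SAP Section 1 says the SAP's definitions override the protocol's.

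**The concern.** A CIF takes each subject's first event. The date named in the definition is the day of withdrawal, and a competing event carries its own, later date. If a competing event falls inside the 30 days and the drug stays off, a program that follows the text finds the withdrawal first and scores a success. Three courses fit this:

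- **Relapse.** All immunosuppression is stopped and relapse of the underlying malignancy is documented on day 14. This is a success in tests 2 and 3. Protocol Section 1.1.2 describes available therapy as "broad-spectrum immunosuppressants which increase the risk of infections and tumor relapse by inhibiting GVT immunity", which gives a reason to stop it when relapse is suspected. That step is my inference; the protocol does not describe it.
- **Progression.** cGVHD progresses on day 20 and neither steroids nor another IST is restarted. This is a success in tests 2 and 3.
- **Switch.** Steroids stop and a non-steroid systemic cGVHD therapy starts on day 10. This is a success in test 2 only.

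The competing-risk list and the Lee row suggest that none of these is meant to count as a successful withdrawal. The tests concerned come directly after the primary and decide whether tests 4 to 6 are reached.

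**Working it through.** **1. Classification under the literal text.** Event within 30 days after 0 mg (test 3: after 0 mg and all ISTs stopped):

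| Event in the window | Test 2 | Test 3 |
|---|---|---|
| Relapse, nothing restarted | success | success |
| Progression, no steroid or IST restarted | success | success |
| Progression or flare, steroids restarted | not a success | not a success |
| New non-steroid systemic immunosuppressant for cGVHD | success | not a success |
| Death | 30 days not completed | 30 days not completed |

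Row 3 follows because a restart breaks the sustained period, and Protocol Section 5.3.2.2.2 permits prednisone re-escalation for flares. In row 4, test 3 fails because the new drug is itself an IST. Protocol Section 6.1.2 treats added cGVHD therapy that way: "Addition of any other new systemic immunosuppressant therapy (including ECP) to treat cGVHD is prohibited".

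**2. Can the dates collide?** Protocol Table 4 reaches zero at Week 24, counted from Week 0 at the first prednisone dose. The Week 25 visit is also 24 weeks after Week 1 Day 1. Appendix A allows the Week 25 response assessment from 7 days before to 21 days after. For a subject who starts prednisone on Day 1 and keeps to the schedule, a formal cGVHD assessment therefore falls between 7 days before and 21 days after 0 mg, largely inside the window. The protocol expects considerable variation in the taper, so this shows only that collisions are plausible.

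**3. Size.** The plan gives no rate, event count or power for these endpoints. Its only sample-size figure is for the primary: [1.960 × √(2 × 0.40 × 0.60) + 0.842 × √(0.21 + 0.25)]² / 0.20² = 93 per arm, or 186. This reproduces and is not affected.

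For the withdrawal endpoints, let W be the share first reaching 0 mg by 12 months, and q the probability of a competing event without restart in the next 30 days. The share reclassified is W × q. Both inputs are assumptions. With 193/2 = 96.5 subjects per arm and W = 50%:

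- q = 2%: 1.0 point, about 1 subject per arm
- q = 5%: 2.5 points, 2.4 subjects
- q = 10%: 5.0 points, 4.8 subjects

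Over W = 30% to 70% and q = 1% to 15%, the range is 0.3 × 0.01 = 0.3 points to 0.7 × 0.15 = 10.5 points.

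To tie q to a yearly risk, assume a constant competing-event hazard h = −ln(1 − R)/365 for one-year risk R, so q = 1 − exp(−30h). Assume also that 0 mg is first reached at day 112 plus an exponential time with mean 250 days. Simulating one million subjects per scenario gives these 12-month CIFs:

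| R | q | Literal rule | Event-free window, dated at withdrawal | Dated at day 30 |
|---|---|---|---|---|
| 20% | 1.8% | 55.7% | 54.7% | 51.1% |
| 40% | 4.1% | 47.2% | 45.3% | 42.6% |
| 60% | 7.3% | 37.4% | 34.7% | 33.0% |

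The fourth column is the third times (1 − q); for example, 47.2 × 0.959 = 45.3. The literal rule therefore adds 1.0, 1.9 and 2.7 points.

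**4. Effect on the comparison.** The between-arm difference moves by W_A q_A − W_B q_B. It is zero if the affected share is the same in both arms. With W = 50% in both and q of 5% against 10%, it is 0.5 × (0.10 − 0.05) = 2.5 points, in either direction.

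**The case against.** The strongest reply is that the SAP never says such a subject counts as a success. The endpoint cannot be established until 30 days have passed, a competing event on day 14 or 20 comes before that, and the competing-risk sentence sits in the same cell. A programmer could reasonably score the competing event. This stands in part: day-30 dating is a possible reading, and a reader should not infer that the SAP deliberately credits failures. But the date the text names is the withdrawal date and it gives no order of precedence, so two defensible programs could give different results for gated tests.

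A second reply is that the cases are few. Flares may be treated by re-escalating prednisone, which removes the success. Appendix I makes assessments that coincide with a flare inevaluable. Protocol Section 5.3.2.4 calls for slow tapering after long-term use. All this narrows the affected group to relapse, progression without restart, and, in test 2, a switch to a non-steroid agent. It does not empty it.

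A third reply is that the study is double-blind and the definition is the same in both arms. That is correct. A reader might infer type I error inflation or a bias towards ibrutinib, but the documents support neither. Applying one rule to both arms changes what the event means and the level of the CIF; it biases the difference only if the affected share differs by arm, and nothing in the documents shows that it does.

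**Conclusion.** The concern holds as a gap in the event definition that, on the literal text, misclassifies some subjects in tests 2 and 3. It covers relapse and progression without restart in both tests, and a switch to a non-steroid systemic cGVHD therapy in test 2 only. It would be too strong to say that any change of therapy is credited in both tests, because a new systemic immunosuppressant already fails test 3 and restarted steroids fail both.

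The likely size is modest: about 1 to 3 points on the 12-month CIF at assumed one-year competing-event risks of 20% to 60%, and 0.3 to 10.5 points over the wider assumed grid. Every rate behind these figures is an assumption. The point merits action because the tests are gated and the correction needs no new data.

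**What to change.** Before unblinding, add one sentence to each of the two rows of SAP Table 2. Withdrawal counts as an event, dated at withdrawal, only if the subject is alive and free of relapse, cGVHD progression and subsequent cGVHD therapy throughout the 30 days; otherwise the competing event is scored at its own date. The sentence should also say how a subject with fewer than 30 days of follow-up after withdrawal is handled.

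Use day-30 dating as a sensitivity analysis only. It might look equivalent, but it also delays every genuine success by 30 days and so lowers the 6- and 12-month estimates. In the scenarios above, the 12-month CIF is 51.1% rather than 54.7%, 42.6% rather than 45.3%, and 33.0% rather than 34.7%.

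The cost is two sentences and a programming condition on dates the analysis already needs. The downside is slightly lower withdrawal rates in both arms.
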